#### 10.3.2 Pregnancy Tests

For all females, a urine pregnancy test will be conducted as scheduled. A negative pregnancy test result must be reported within 24 hours prior to the first dose of study drug.

### 10.4 Reporting of Safety Laboratory Tests

The results of Safety Laboratory Tests will be returned to the Investigator as quickly as possible, typically within 48 hours. Reference ranges (lower limit of normal, upper limit of normal; by sex and age, if appropriate) will be provided for the CBC.

Procedures for the investigator assessment of laboratory results are detailed in Section 12.1.5.

#### 10.4.1 Repeating Abnormal Laboratory Tests

A CBC showing abnormal or clinically significant values at screening may be repeated no more than once. After dosing, an abnormal CBC assessed as “clinically significant” values may be repeated as often as deemed clinically necessary by the Investigator until the test values return to clinically acceptable limits or until an explanation other than drug effect is given.

### 10.5 CBC.

A 4 ml phlebotomy will be performed to obtain blood for a CBC, kept in a cooler at 20-22 C and transported to the clinical laboratory for the study.

### 10.6 Interferon Gamma Release Assay (IGRA)

A 4-6 mL phlebotomy will be performed to obtain blood for the IGRA (T spot, Oxford Immunotec, Oxford, UK). Blood will be immediately placed in a cooler at 20-22 degrees C and transported within 4 hours to the DarDar Laboratory. Processing will be completed within 32 hours of collection according to

manufacturer's instructions and results will be interpreted as positive or negative according to manufacturer's instructions.

#### **10.7 RNA Expression**

A 2.5 mL phlebotomy will be performed 7 days after Dose 3 using a Paxgene tube. Samples frozen at -80C, batched and stored at MUHAS for later processing to compare differences in RNA expression between vaccine and placebo recipients.

### **11. STUDY EVENTS**

Detailed schedules of evaluations are shown Section 2.9. The schedule is presented relative to the day and time of dosing. All Days are relative to day of first injection of study drug, designated Day 0; all times are relative to the most recent injection, designated 0 hr.

***Monitoring for adverse events and concomitant medications will be performed on an ongoing basis from screening through End-of-Study visit.***

#### **11.1 Screening**

The screening evaluation may be performed up to 28 days prior to dosing. The subject will sign an Informed Consent/Assent Form before any study-specific procedures are performed.

The subjects will receive a printed version of the signed informed consent for their records.

#### **11.2 End-of-Study Visits For Subjects who Terminate Prematurely**

Subjects who terminate prematurely, for any reason, should have a final safety visit completed at approximately 30 days after the last dose received, or if that timepoint is already passed, as soon as possible. This final visit should include phlebotomy for an IGRA assay. If they cannot complete a visit, safety follow-up should be conducted by phone.

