### 2.4.1 Enrollment Process

As part of the overall risk management plan enrollment will proceed as follows:

- All adolescent subjects will provide written assent and their parents or guardians will provide written consent. Informed consent and assent forms will be written in Kiswahili and will be explained by a study nurse.
- Urine pregnancy tests will be performed on all female subjects on the day of scheduled immunization. Those with positive tests will be excluded from further immunization but will continue in follow-up.

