## 2.9 Schedules of Study Events

**Table 1. Schedule of Study Events –**

Event / Evaluation	Visit #	Screen	1			2			3			4	5,6
			0		+7	60 a (46-74)		+7	120 a (106-134)		+7		
			Day	Hour	Pre	0	0.5	Pre	0	0.5	Pre	0	0.5
Informed Consent/Assent		X											X
Risk factor interview		X										X	X
Examination for BCG scar		X											
Vital signs, height and weight		X	X		X	X	X	X	X	X	X	X	X
Examination of injection site d					X	X	X	X	X	X	X	X	X
Complete blood count (CBC)		X		X		X					X		X
Urine pregnancy test (F only)						X			X			X	
IGRA e,f,g		X				X						X	X f
RNA expression											X		
Dose administration					X			X			X		

a Numbers in parentheses provide range that is acceptable

b 14 month visit can be performed at 13-15 months

c 24 month visit is **end of study (EOS)** and can be performed at 22-24 months

d Day 7 injection site examination can be performed on day 6-8 after injection.

e Blood volume for T-spot IGRA = 6 mL, blood volume for CBC = 4 mL; blood volume for RNA expression = 2.5 mL; total blood volume for study = 42.5 mL (+ or - 20%)

f Subjects with a new positive IGRA **at the end of study** or at Visit 5 will need a repeat IGRA at  $\geq$ 3 months later

g Subjects will be reconsented to obtain an additional IGRA at or before 12 months after Visit 5

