### 7.5.1 Definition of a Dose-Limiting Toxicity (DLT) Event

A DLT *systemic clinical event* is defined as a treatment-emergent systemic clinical event that meets **all** of the following criteria:

- is assessed by the investigator as related or possibly related to study drug (see Section 12.3.3);
- is of severity (see Section 12.3.4) Grade 2 or higher;
- is of duration >48 hours.

A DLT *injection site reaction* (ISR) is defined as an event that meets **both** of the following criteria:

- occurs at the injection site;
- is of severity Grade 3 or higher.

A DLT *laboratory event* is defined as a confirmed, treatment-emergent laboratory finding that meets **both** of the following criteria:

- is **not** considered consistent with a concurrent clinical event that is assessed as not related or unlikely related to study drug (e.g., an accidental injury, new ART); **and**
- based on pre-specified toxicity criteria (see Section xx) represents an increase of two Grades or more compared to pre-treatment baseline value.

A subject who experiences a DLT event will not receive further doses of study drug. Unblinding may be performed to determine if a DLT event has occurred in a subject receiving DAR-901.

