### 7.5.2 Definition of a Completed Patient

A **subject** is considered complete when s/he meets **either** of the following criteria:

- received all scheduled doses of DAR-901 and completes the study visit at 24 months, **or**
- received at least one dose of DAR-901 **and** had treatment discontinued due to a DLT event.

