## 7.6 Procedures for Managing the Study

### 7.6.1 Discontinuing Study Treatment in Individual Patients

Study treatment may be discontinued in an individual patient for **any** of the following reasons:

- The subject withdraws from study participation by their own decision (“withdrawal of consent”); this may happen at any time and for any reason without prejudice for their continued care.
- The subject has a DLT event as defined in Section 7.5.1.
- The Investigator determines, based on their judgment, that discontinuation of study treatment is in the subject’s best interest, e.g., due to an adverse event, noncompliance, or any reason, whether or not related to study drug or study procedures.

If study treatment is discontinued prematurely, the reasons will be recorded and, if possible, the EOS visit will be performed as specified (see Section 11). If a subject cannot be seen, attempts will be made to contact the subject by telephone.

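### The protocol does not separate stopping injections from leaving the study, so following its text could lose the outcome IGRAs of subjects who only stop dosing

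*Protocol*

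**What the plan says.** Section 7.6.1 is about stopping study treatment, whether by consent withdrawal, DLT or investigator decision. It ends: "If study treatment is discontinued prematurely, the reasons will be recorded and, if possible, the EOS visit will be performed as specified (see Section 11").

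Section 11.2 covers subjects who terminate prematurely for any reason. They "should have a final safety visit completed at approximately 30 days after the last dose received", or as soon as possible if that time has passed. It adds: "This final visit should include phlebotomy for an IGRA assay". It does not say whether terminating refers to treatment or to the study.

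Section 7.5.1 says: "A subject who experiences a DLT event will not receive further doses of study drug". Section 7.5.2 offers two routes to being complete. One is all scheduled doses of DAR-901 plus the 24-month visit. The other is at least one dose of DAR-901 in a subject who "had treatment discontinued due to a DLT event", with no visit required.

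Two other places point the other way. On positive pregnancy tests, 2.4.1 says: "Those with positive tests will be excluded from further immunization but will continue in follow-up". Note c to Table 1 defines EOS as the 24-month visit, which is final "and can be performed at 22-24 months".

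The primary endpoint (2.8.3, 14.3) is IGRA conversion after month 2, compared by log-rank test as intention-to-treat. The tests that can show it are at 14 and 24 months (2.4).

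**The concern.** An as-randomized comparison needs the outcome tests whether or not a subject finishes the injections. If stopping injections is handled as leaving the study, subjects who stop lose their later IGRAs. Those who stop before month 2 are removed from the efficacy population altogether, which is a post-randomization exclusion caused by a post-dose event and not ordinary censoring.

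The loss could be related to treatment. Under 7.5.1 a DLT is a systemic event judged related or possibly related (Grade 2 or higher, lasting over 48 hours), an injection-site reaction of Grade 3 or higher, or a two-grade laboratory change. With saline as control, the first two would be expected more often on DAR-901. Section 14.6 says that missing data will in general not be imputed, and a missed IGRA cannot be recovered later.

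**Working it through.** **The text.** Section 7.6.1 can be read in two ways.

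- Reading A: the EOS visit means the early visit in 11.2. In favour: it is the only off-schedule EOS visit in Section 11, it is counted from the last injection, both sections fall back on the telephone, and 7.5.2 asks for no 24-month visit after a DLT.
- Reading B: it means the 22-24 month visit, because Section 11 also refers to the schedule in 2.9. Even so, 7.6.1 asks for that visit only if possible and does not mention the month-2 and month-14 IGRAs.

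No sentence on either reading says that subjects stopped for a DLT or by the investigator keep the IGRA schedule.

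**Consequences under reading A.**

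- Stopped after dose 1 (day 0): exit at about day 30, before the month-2 window (days 46-74). No month-2 IGRA, so outside the efficacy population (14.2) and replaced under 7.6.2. If the stop is decided at Visit 2 itself, the exit IGRA may serve as the month-2 test, but the later tests are still lost.
- Stopped after dose 2 (day 60): exit at about day 90. The 14- and 24-month IGRAs are lost, and the subject is censored about one month after the month-2 test.
- DLT after dose 3 (day 120): no scheduled dose remains to be stopped.

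**Baseline power.** Section 14.1 states 80% power for 50% efficacy with 650 subjects (325 per arm, 2.8.5), 7% annual infection, 5% annual loss and 1.75 years of follow-up. Expected events per arm are n × h/(h+c) × (1 − exp(−(h+c)T)), with c = 0.05 and T = 1.75:

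- placebo (h = 0.07): 325 × 0.07/0.12 × (1 − e^−0.21) = 35.9
- vaccine (h = 0.035): 325 × 0.035/0.085 × (1 − e^−0.14875) = 18.5
- total D = 54.4

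Schoenfeld power is Φ(√(D·a(1−a))·ln 2 − 1.96), where a is the vaccine share. With a = 0.5 it is 72.5%, two-sided. Among the variants tried, the stated 80% came out only with a one-sided 0.05 test (80.2-82.0%). The protocol does not give the sidedness. That is a separate matter; 72.5% serves here only as the baseline.

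**Extra loss in the vaccine arm.** No stopping rate is given for this trial, so a fraction d is assumed, with no extra loss on placebo. The nearest figure is the note to Table 5-9: 12 subjects (1.2%) stopped for reactions possibly or probably due to vaccine. This matches 12/1006 = 1.2% of SRL 172 recipients (Table 5-6). The 5% and 10% rows are assumptions. Unobserved events are 18.5 × d. If the lost subjects have k times the hazard of the rest of the arm and true efficacy is 50%, the observed hazard ratio is 0.5/((1−d) + kd).

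| d | Subjects of 325 | Vaccine events unobserved | Power | Apparent efficacy, k = 2 | Apparent efficacy, k = 0 |
|---|---|---|---|---|---|
| 0 | 0 | 0 | 72.5% | 50% | 50% |
| 1.2% | 3.9 | 0.2 | 72.3% | 50.6% | 49.4% |
| 5% | 16.2 | 0.9 | 71.7% | 52.4% | 47.4% |
| 10% | 32.5 | 1.9 | 70.9% | 54.5% | 44.4% |

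Example at 1.2%: 0.5/(0.988 + 0.024) = 0.494 for k = 2, and 0.5/0.988 = 0.506 for k = 0. With k = 1 apparent efficacy stays at 50%.

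**The case against.** The best defence is reading B together with 2.4.1: the protocol already keeps some subjects in follow-up after dosing stops, 11.2 fits people leaving the study, and it secures an exit IGRA. Reading B is tenable, so the early exit cannot be called the protocol's settled rule. The need to reconcile the passages stands, because neither reading secures the scheduled tests after a DLT or an investigator's stop.

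Four stronger inferences are tempting, and the documents do not carry them.

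- *The loss is nearly all on vaccine.* More loss on vaccine is plausible, but no rate by arm is given. Stops by consent withdrawal need not differ: the note to Table 5-9 reports 65 self-withdrawals, 35 on SRL 172 and 30 on placebo. Phase 1 saw no severe injection-site reactions (5.4.1), and its largest 1 mg reaction was 20 mm (Table 4), against more than 10 cm for Grade 3 by size (Table 12-5).
- *Up to a quarter of the vaccine arm could be lost.* In the Finnish study 5 of 19 HIV-positive recipients withdrew (26%), but all after dose 3 or 4 (Table 5-8). None stopped before a three-dose series would have ended. Even the 1.2% comes from a five-dose schedule.
- *Those who react are the strongest immune responders.* The protocol has no data on this, so the direction of any bias is unknown.
- *The completion label removes data.* It defines no analysis population in 14.2. It can hide missing outcomes in disposition counts, and as worded no placebo subject can meet either route.

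**Conclusion.** The concern holds as an inconsistency. Sections 7.6.1, 11.2 and 7.5.2 do not distinguish stopping injections from leaving the study. Followed on one reasonable reading, they lose IGRAs that the as-randomized analysis needs. They fit badly with 2.4.1 and with EOS as defined in Table 1.

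The likely size is small. At 1.2%, about 4 of 325 vaccine subjects and 0.2 expected events are affected, power moves by about 0.2 points, and apparent efficacy moves by about 0.6 points in either direction if the lost subjects have twice the hazard or none. At an assumed 10%, power falls by 1.6 points and apparent efficacy shifts by about 5 points, up or down. These figures assume reading A, loss confined to the vaccine arm, and no outcome information at all from those who stop. They are a guide to scale and not a forecast. The case for acting is that the loss may be treatment-related, cannot be repaired afterwards and is cheap to prevent.

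**What to change.** Reconcile the passages as follows.

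- In 7.6.1 and 11.2, state that subjects who stop injections without withdrawing consent stay in follow-up and have every remaining scheduled IGRA, including month 2 where it is still due. Keep the 30-day contact as an added safety visit for them, and limit the final visit of 11.2 to subjects leaving the study.
- In 7.5.2, define study completion by the 24-month visit and report treatment completion separately. Refer to doses of study treatment instead of DAR-901, so that placebo subjects can qualify.
- Report completeness of the 14- and 24-month IGRAs by arm.

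The cost is amendment wording and a few visits already on the schedule. No rule on when treatment stops is changed.

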## 12. SAFETY EVALUATIONS

Clinical trials sponsored by Dartmouth College will be conducted in accordance with Good Clinical Practices for collecting and reporting safety information. Safety and tolerability will be evaluated based on AEs, vital signs, physical exams, laboratory tests and other assessments.

### 12.1 Definitions

#### 12.1.1 *Adverse Event (AE)*

An Adverse Event is any untoward medical occurrence temporally associated with the use of a medical product in a subject, *whether or not* the event is considered causally related to the medical product. An AE can be a new occurrence or an existing process that increases significantly in intensity or frequency.

An AE in a clinical trial may be *any* of the following:

- Unfavorable and unintended *symptom reported by the subject* — subjects will be encouraged to report treatment-emergent AEs spontaneously; general, non-directed questioning may also be used to elicit reports of AEs;
- Clinical *sign detected by the Investigator* — observations by other study personnel will be reported to the Investigator for evaluation;
- Is a treatment-emergent new or increased abnormal result from a *laboratory study* or other *diagnostic procedure*.

#### 12.1.2 *Pregnancy*

Pregnancy is not an AE. Pregnancy testing will be performed as scheduled. If a female subject becomes pregnant during a study, the Medical Monitor must be notified in writing within five days. Follow-up information regarding the outcome of the pregnancy and any postnatal sequelae in the infant will be obtained.

#### 12.1.3 *Serious Adverse Event (SAE)*

An AE is **serious** when the subject outcome is one or more of the following:

- Death.
- Life-threatening, meaning that the subject was at immediate risk of death from the event at the time that the event occurred. It does not include an event which hypothetically might have caused death if it occurred in a more severe form.
- Hospitalization, initial or prolonged, meaning that a hospital admission and/or prolongation of a hospital stay was required for the treatment of the AE, or occurred as a consequence of the event. It does not include a pre-planned elective hospital admission for treatment or diagnostic procedures, or, in general, a hospital admission of less than 24 hours duration.
- Disability or incapacity that is persistent or significant.
- Congenital anomaly or birth defect.
- Important medical event that, although not immediately life-threatening, requires intervention in order to prevent one of the other serious outcomes listed above. Examples of such events are allergic bronchospasm requiring intensive treatment in an emergency room or at home; blood dyscrasias or convulsions that do not result in hospitalization; or the development of drug dependency or drug abuse. For the present study a new case of active tuberculosis will be considered an SAE in this category.

 A medical product may be a drug or a device being used either prior to or after regulatory approval. The medical product in this protocol will hereafter be referred to as study drug (synonym: investigational agent).

#### **12.1.4 Suspected, Unexpected Serious Adverse Reaction (SUSAR)**

A SUSAR is defined as an SAE that meets **both** the following criteria with respect to study drug:

- *Suspected* — is assessed as related or possibly related to study drug (see Section 12.3.3);
- *Unexpected* — compared to the study drug-related AEs described in Investigator's Brochure, the event meets *any* of the following criteria:
  - The event was not previously described;
  - The event is now characterized as more severe (see Section 12.3.4);
  - The event is now characterized more specifically (e.g., an event of "interstitial nephritis" in a subject receiving an agent previously described as associated with "acute renal failure").

In clinical trials involving ill patients, events considered related to the natural history of the disease under study or to lack of efficacy (that is, the event is considered more likely related to those factors than to other factors, including study drug) are not considered "unexpected". Lack of efficacy is recorded as specified elsewhere in the Protocol.

#### **12.1.5 Investigator Assessment of Safety Laboratory Tests**

The Investigator will review the results of the CBC (see Section 10.3.1 and Section 10.3.2) and designate any results outside of the reference range as *either* of the following:

- Abnormal, not clinically significant (NCS)
- Abnormal, clinically significant (CS).

In making this judgment, the Investigator will consider all available information, including the patient's clinical condition, all available laboratory results (central and local), and the potential for false positive test results. In addition, laboratory studies that result in the actions specified in Section 12.1.1 will be classified as "abnormal, clinically significant".

Any result assessed as "abnormal, clinically significant" will be recorded as an AE *unless* it is consistent with one or more of the following:

- Process noted in the medical history.
- Ongoing adverse event already recorded;
- Expected course of the primary disease under study (if applicable);

### **12.2 Collecting and Recording Adverse Events**

Procedures for the collection and recording of AEs are as follows:

- At all study visits subjects will be questioned using both a scripted checklist to elicit anticipated vaccine-related adverse events, as well as open-ended queries to elicit unanticipated events.
- After the EOS, surveillance will be passive (only events brought to the investigator's attention will be considered) and only events assessed as SUSARs will be recorded.

### **12.3 Characterizing Adverse Events**

For each AE recorded the following characteristics will be noted.

#### **12.3.1 Description of Event**

The diagnosis or description will be as specific and complete as possible (i.e., "lower extremity edema", rather than just "edema"). Whenever possible, signs and symptoms due to a common etiology will be reported as an integrated diagnosis; for example, cough, runny nose, sneezing, sore throat and head congestion would be reported as "upper respiratory infection".

### 12.3.2 Date and Time of Onset

The date and time at which the event was first apparent. Table 12-1 summarizes the basis for reporting the date and time of onset for the different types of AEs described in Section 12.1.1.

**Table 12-1. Reporting the Date and Time of Onset of AE for Different Types of Events**

Type of Event	Examples	Source of Date and Time of Onset
Symptom	Headache, feverish, paresthesias	When first experienced by the patient
Sign (Finding)	Elevated BP, enlarged liver on physical exam	When first observed by the Investigator or other study staff
Laboratory / diagnostic result	Neutropenia, hyperglycemia, lesions on brain scan	When lab sample was obtained or diagnostic study performed

The time of onset of symptoms may be appreciably earlier than the date and time the Investigator becomes aware of the event. Some events may be apparent to the patient and Investigator independently, and information from each may contribute to the final report. For example, a patient may report the onset of a rash two days before being seen by a physician who makes a diagnosis of herpes zoster based on appearance and laboratory confirmation. In that case, there is a single AE, with the date of onset based on the date of the initial observation by the patient and a specific description (herpes zoster) based on the clinical exam and tests.

### 12.3.3 Relationship to Study Drug

This determination is based on the Investigator's clinical judgment and the Medical Monitor's clinical judgement regarding the likelihood that the study drug caused the AE and may include consideration of some or all of the following factors:

- Alternative possible causes of the AE, including the subject's underlying disease or co-morbid conditions, other drugs, other host and environmental factors;
- Temporal sequence between the exposure to study drug and the AE;
- Whether the clinical or laboratory manifestations of the AE are consistent with known actions or toxicity of the study drug;
- Whether the AE resolved or improved with stopping the study drug (i.e., dechallenge); or recurred or worsened with re-exposure to the drug (i.e., rechallenge).

The relationship between the study drug and the AE will be described using one of the following categories:

- **Related** — the study drug is more likely the cause of the AE than other factors;
- **Possibly related** — there is a *reasonable* possibility that the study drug is the cause of the AE, including that the study drug and another factor(s) are equally likely as causes of the AE;
- **Unlikely related** — another factor is considered more likely the cause of the AE than the study drug;
- **Not related** — another factor is considered to be the cause of the AE.

Related or possibly related AEs may result during the use of the study drug as planned (per protocol), or from abuse, withdrawal or over-dosage of the agent.

